### ***Step 7: Assessment post-intervention (T2) – Week 25***

After 15 weeks, the three questionnaires on self-efficacy, aggression and treatment readiness will be administered again, following the same procedures as described before. Furthermore, after finishing the final lesson of the intervention, the patient will fill out the TWEETS on the Minddistrict platform.

### ***Step 8: Qualitative data collection with patients - Week 25 – 30***

After the intervention is completed, a randomly selected sample of patients is invited to participate in a post-intervention interview. This sample is generated by means of (<https://sealedenvelope.com/>). Because the perspective of patients who dropped out of the intervention also is very relevant, the target group of this interview study will consist of patients who completed at least one session of the intervention, i.e. who completed the first TWEETS. Additionally, patients still have to be treated at the outpatient clinic in order to participate. Semi-structured interviews will be conducted in-person or via videoconferencing, depending on the preference of the patient and practical limitations.

### ***Step 9: Follow-up assessment (T3) – week 37***

37 weeks after start of treatment, the three questionnaires (self-efficacy, aggression and treatment readiness) will be again administered via Qualtrics. If, at this point, the patient is not being treated at the outpatient clinic anymore, he or she will be contacted by the researchers. This will be clearly communicated in the informed consent form and by the therapist. The FARE that will be administered about 6 months after treatment as part of standard assessment by clinics will be used for the follow-up assessment. Participants will receive the second €10 voucher after completing the this final assessment.

**Step 9: Qualitative data collection – therapists**

An open-ended questionnaire will be sent to all participating therapists at the final stages of the study period, i.e. in Q2 2023. In this questionnaire, they will be asked about their experiences with the internet-based interventions.

**8.4 Time investment of participants**

Participants in the experimental and control condition fill out three short questionnaires per measurement moment. This is estimated to take a maximum of 15 minutes. Data collection is kept short intentionally: forensic psychiatric patients are generally considered as hard to involve in research due to low motivation and short attention spans. To increase the feasibility of data collection, only the most relevant questionnaires from a clinical and research point of view are used. Additionally, patients in the experimental condition individually work on the intervention outside of in-person treatment sessions. On average, this is estimated to take about 30 minutes per weekly lesson, but experiences in practice show that this can either take much longer or shorter, depending on the patient and lesson. Furthermore, to increase the feasibility of this study, participants will be compensated for their invested time by means of a voucher of €10 after the mid-treatment assessment (T1) and another voucher of €10 the final post-treatment assessment (T3). Experience with research with this target group has shown that financial rewards can serve as a motivator to participate and complete the study.

**Timeline**

Depending on the timing of ethical approval, inclusion of participants will start in April 2022 up until February 2023. This means that the final follow-up assessment can take place up until September 2023. Participants will start with the study at any point during between Q2 2022 and Q2 2023. To illustrate: the first participant can start with the study in April 2022, while the last participant can start 8 months later. In the meantime, there will be no changes to the internet-based intervention 'Aggression' to ensure consistency. This procedure ensures that patients do not have to wait to start treatment and also increases the feasibility of this study: including participants in forensic mental healthcare has been shown to be challenging.

**8.5 Withdrawal of individual subjects**

Subjects can leave the study at any time for any reason if they wish to do so without any consequences. The investigator can decide to withdraw a subject from the study for urgent medical reasons. Patients can also be withdrawn in case of a severe psychiatric crisis and/or admission to a (forensic) psychiatric hospital, other type of inpatient clinic, or prison.

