## 4. STUDY POPULATION

### 4.1 Population (base)

#### *Description of the population base*

Forensic mental healthcare is focused on people who display aggressive or sexual delinquent behaviour that led or could lead to offending and simultaneously suffer from at least one psychiatric disorder, for example schizophrenia, alcohol abuse, antisocial personality disorder or post-traumatic stress-disorder [1-3]. Due to this combination of offending and psychiatric disorders, forensic mental healthcare - or forensic psychiatry - takes place at the intersect of mental healthcare and the law. Forensic mental healthcare encompasses treatment of both in- and outpatients. Inpatients reside in clinics with different levels of security, ranging from very high levels, where patients are not or almost never allowed to go on leave, to medium or low levels, where patients have more freedom and independence [37]. While relatively many forensic psychiatric patients receive treatment at inpatient clinics, a large share of the patient population comprises outpatients who live at home and receive treatment at an outpatient clinic [38]. Some patients receive treatment voluntarily and not as part of a sentence, for example when a general practitioner refers them to forensic mental healthcare because it fits their aggression regulation problems better than regular mental healthcare. Regardless of the differences between security levels, the main goal of forensic mental healthcare is always to prevent (re)offending and thus to protect society. Treatment of forensic psychiatric patients is viewed as challenging, which can be partly explained by characteristics of the patient population: most forensic psychiatric patients are not that motivated for their treatment [4, 5]. Furthermore, they often have followed no or very little education and many patients have low literacy levels [6-8]. Additionally, co-morbidity is common: patients often have multiple psychiatric disorders [9]. In general, the forensic psychiatric patient population is very heterogeneous, but the main common factor is that for all patients, there is a risk on (re)offending.

This study is focused on people that receive forensic psychiatric outpatient care with a primary focus on aggression. To increase the feasibility and generalizability of this study, inclusion takes place at four large forensic psychiatric organizations that all treat patients at multiple outpatient clinics.

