### **8.7 Follow-up of subjects withdrawn from treatment**

If patients withdraw from treatment entirely, they will be excluded from the study. The main reason for this is that the internet-based intervention has to be studied within the context of treatment, i.e. in a blended way. If participants in the experimental or control group do not receive treatment anymore, their data will not be relevant for the research questions of this study. As mentioned before, patients that stop using the intervention but still participate in data collection will not be considered as drop-outs.

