## 10. STATISTICAL ANALYSIS

### 10.1 Primary study parameter(s)

Data will be analysed using IBM SPSS software (version 24.0) and significance was accepted at 0.05 or lower. Analyses will be done on intention to treat (ITT) basis.

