#### ***Research objective 1: Self-efficacy, treatment readiness, and aggression***

To identify whether there are changes in dependent variables between the experimental and control group on baseline (T0), during the intervention (T1), post-intervention (T2) and follow-up assessment (T3), multilevel repeated-measures linear mixed models will be used. This analysis method accounts for autocorrelation within participants and missing data. Time and group will be used as fixed factors, along with their interactions, and participants are modelled as random factor. Interaction effects will be studied to identify whether the changes over time differed between groups. Main effects for time will be used to investigate whether the scores of all participants changed over time. In order to provide more insight into the main findings, Least-significant difference (LSD) post-hoc independent t-tests with Bonferroni correction will be performed to test for significant between-group differences and changes over time per group.

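### Section 8.5 lets patients be withdrawn from the study after a crisis, admission or imprisonment, so later scores can be lost for outcome-related reasons with no sensitivity analysis planned

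*Combined protocol and SAP*

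**What the plan says.** Section 8.5 first allows the investigator to withdraw a subject from the study for urgent medical reasons. It then adds: "Patients can also be withdrawn in case of a severe psychiatric crisis and/or admission to a (forensic) psychiatric hospital, other type of inpatient clinic", with prison as the last item. It does not say who decides in these cases, by what criteria, whether questionnaires are still offered afterwards, or what happens to scores already collected.

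Four other places bear on it:

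- Section 10.1 states: "Analyses will be done on intention to treat (ITT) basis". The analysis set is not defined. Of the linear mixed model, the same section says: "This analysis method accounts for autocorrelation within participants and missing data". No missing-data assumption is named and no sensitivity analysis is planned.
- Section 8.7 has a stricter rule for a different group: "If patients withdraw from treatment entirely, they will be excluded from the study". For participants no longer receiving treatment it adds that "their data will not be relevant for the research questions of this study".
- Section 8.3, Step 9 points the other way for T3: "If, at this point, the patient is not being treated at the outpatient clinic anymore, he or she will be contacted by the researchers".
- Sections 4.4 and 8.6 allow for 20% drop-out, defined by unanswered questionnaires whatever the reason.

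**The concern.** The trial judges the module on emotional self-efficacy, treatment readiness and aggression, with the T3 comparison deciding whether it is called effective (section 10.1, Determining effectiveness). Section 4.1 says that "the main goal of forensic mental healthcare is always to prevent (re)offending and thus to protect society". The FARE (section 8.1.2) scores impulse control, coping, substance use, living situation and rule-violating behaviour. A patient who is imprisoned, admitted or in severe crisis is likely to be doing worse on several of these. If that patient's follow-up ends because of the event, poor T3 scores are selectively missing.

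The trial is non-blinded (section 8.2) and withdrawal is optional, so the rule may be applied differently in the two arms. If more poor scorers are lost from the control arm, a benefit is understated. If more are lost from the experimental arm, the module looks better than it is.

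**Working it through.** **Plan's own figures.** For d = 0.5, two-sided alpha 0.05, power 0.80 and an independent t-test (section 4.4), the exact calculation gives 63.77, so 64 per arm and 128 in total, as stated. The target of 154 is 128 × 1.2 = 153.6. This allowance covers how many patients are lost. It cannot correct for which patients are lost.

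**Inputs not in the documents.** No rate of crisis, admission or imprisonment is given, nor any score difference for such patients. Assumed here: withdrawal rates differing between arms by 0 to 10 points, and withdrawn patients scoring m = 0.5 to 1 SD worse than retained patients in the same arm.

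**Bias if these patients are dropped entirely.** In each arm the full mean equals the retained mean minus p × m. With the same m in both arms, the bias in favour of the experimental arm is

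bias = (pE − pC) × m

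| Withdrawn, E vs C | m = 0.5 SD | m = 1 SD |
|---|---|---|
| 10% vs 10% | 0 | 0 |
| 10% vs 5% | 0.05 × 0.5 = 0.025 | 0.05 × 1 = 0.05 |
| 15% vs 5% | 0.10 × 0.5 = 0.05 | 0.10 × 1 = 0.10 |

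Swapping the arms reverses the sign. The range is 0 to 0.10 SD, and 0.10 / 0.5 = 20% of the target effect. If m differs by arm, the bias is pE × mE − pC × mC, so equal rates alone do not guarantee zero: 10% in each arm with deficits of 1 and 0.5 SD gives 0.10 − 0.05 = 0.05 SD.

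**Bias if earlier visits are kept.** This is closer to what the mixed model does under section 8.5. A large-sample simulation used a true difference of 0, a correlation of 0.6 between visits, and withdrawal depending on the T3 score itself (logit slope 1.5):

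| Withdrawn | Dropped entirely | Earlier visits kept |
|---|---|---|
| 5% vs 10% | 0.06 SD | 0.04 SD |
| 5% vs 15% | 0.11 SD | 0.06 to 0.07 SD |
| 10% vs 20% | 0.11 SD | 0.06 SD |
| 10% vs 10% | 0 | 0 |

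The withdrawn patients in this simulation average about 0.9 to 1.2 SD below their arm's full mean. It therefore represents the upper end of the assumed deficits or slightly beyond. The earlier visits remove part of the bias, not all of it.

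**Effect on the test.** With 64 per arm, SE = √(2/64) = 0.177 SD. The two-sided error rate under a bias b is 1 − Φ(1.96 − b/SE) + Φ(−1.96 − b/SE). This gives 5.9% for b = 0.05 and 8.7% for b = 0.10, against the nominal 5%. A larger sample would not remove the bias.

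**The case against.** A reader might infer that section 8.5 takes treatment failures out of the dataset and so breaks ITT outright. The text does not support that. It says patients can be withdrawn, and nothing about deleting what they have already answered. A mixed model can use every score up to withdrawal. The wording about exclusion and irrelevant data is in section 8.7, for patients who leave treatment. Many admitted or imprisoned patients may also fall under that section, but a patient in crisis who remains in outpatient care would not, so section 8.5 needs its own correction.

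Other points have weight:

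- The endpoints are questionnaires and a risk instrument. Admission and imprisonment are not endpoints, and an admission may have nothing to do with aggression. The link to outcome is an inference from the aims of treatment.
- The assumed rates have no source. Attributing 10 to 15% in one arm to these events takes half to three quarters of the 20% allowed for all causes. Patients with current psychosis and inpatients are excluded at entry (section 4.3), and the study is introduced only after about eight weeks of treatment.
- Step 9 already plans T3 contact with patients no longer treated at the clinic.
- Answers from a ward or prison describe behaviour in another setting, and some patients cannot be reached.

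These points limit the size and certainty of the concern. They do not supply the missing follow-up rule or the missing sensitivity analysis.

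**Conclusion.** The concern holds as a missing-data weakness. Section 8.5 allows outcome follow-up to end, at the discretion of people who may know the allocation, because of events plausibly related to the outcomes. The only protection is a mixed model whose assumption is least convincing for these patients and is never tested. That fits poorly with an unqualified ITT statement but is not a proven breach of it.

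The bias is 0 to 0.10 SD if these patients are dropped entirely, under the assumed rate differences of 0 to 10 points and deficits of 0.5 to 1 SD. It is smaller if earlier visits are kept: about 0.04 to 0.07 SD in the simulated cases with 5 to 10 point differences. It is nil when rates and deficits are the same in both arms. A reader might also infer a guaranteed minimum bias or a known direction; with no event rates in the documents, neither can be claimed. The change is worth making because it is cheap and leaves care decisions untouched.

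**What to change.** 1. State in section 8.5 that, whatever is decided about care, these events do not end outcome follow-up unless the patient withdraws consent.
2. Define the ITT set in section 10.1 as all randomised patients, and keep every score collected.
3. Continue to offer the T1 to T3 questionnaires where the patient can be reached, extending what Step 9 already plans for T3.
4. Report by arm the number of patients withdrawn after crisis, admission or imprisonment, with the reason and the last assessment completed.
5. Add a delta-adjusted sensitivity analysis in which these patients' missing T3 scores are set 0, 0.5 and 1 SD worse than predicted. The shifts should be varied separately by arm, because equal shifts with equal losses barely move the contrast.
6. Reconcile section 8.3 (Step 9), section 8.5, section 8.7 and section 10.1, so that one rule says who is followed and whose data are analysed.

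The cost is protocol and SAP wording, a simple log of reasons, and one further analysis. The questionnaires are already online and take at most 15 minutes (section 8.4). Some patients will remain unreachable, and answers given in a ward or prison will need cautious interpretation.

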### **8.6 Replacement of individual subjects after withdrawal**

To account for withdrawal of subjects, 20% more participants than required according to the power analysis will be included. If patients drop-out, this will be accounted for due to this extra 20%. Patients are considered as a drop-out if they stop filling out the questionnaires before the end of the study. Consequently, if patients stop using the intervention but still fill out the questionnaire, they are not considered a drop-out. A reason for this is that investigating whether non-adherence to these interventions is problematic and related to engagement or effectiveness is part of this study. Data collection will be ended after including the intended 154 patients. If throughout the study, there are signs that more than 20% of the patients drop out, the researchers will re-evaluate the feasibility of the data collection with participating therapists and search for points of improvements.

### **8.7 Follow-up of subjects withdrawn from treatment**

If patients withdraw from treatment entirely, they will be excluded from the study. The main reason for this is that the internet-based intervention has to be studied within the context of treatment, i.e. in a blended way. If participants in the experimental or control group do not receive treatment anymore, their data will not be relevant for the research questions of this study. As mentioned before, patients that stop using the intervention but still participate in data collection will not be considered as drop-outs.

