#### 4.4 Sample size calculation

This sample size calculation is conservatively based on the ability to detect at least a moderate effect of Cohen's  $d = .50$  on the primary outcomes at follow-up (T3). A power analysis was conducted with G\*power. The analysis was conducted with a moderate effect size of 0.5, a  $\beta$ -power of .8, a p-value of 5%, and an independent two-sided t-test as method of analysis. This analysis showed that 64 patients need to be included in each condition. This means that a total of 128 patients needs to be included. Accounting for a drop-out of 20%, the goal for inclusion is set at a total of 154 patients. It is important to note that participants in the experimental condition are considered as a 'drop-out' when they don't fill out the questionnaires at all measuring moments, not when they stop using the intervention. In other words: patients can stop using the intervention. In other words: patients can stop using the intervention, but can still complete their participation in the study if they fill out all questionnaires. Adherence to the intervention is not the same as drop-out from the study, since it is a different concept. The main reason for this is that earlier research has shown that patients often stop using these interventions before all lessons are completed, so it is not realistic to expect that all patients fully complete the intervention. In order to account for this, the number of completed lessons will be included as a moderator for effectiveness in the analyses to investigate whether adherence is related to effectiveness. Additionally, a sub-goal of this study is to determine whether engagement is a predictor of adherence and effectiveness to incorporate non-adherence to the intervention in the study. The intended 154 patients will be included at four different organizations that all have multiple forensic outpatient clinics.

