### **8.8 Premature termination of the study**

Based on the absence of risk associated with using internet-based interventions in treatment – which have been used in Dutch outpatient treatment for over ten years, without any incidents – we expect that there will be no reason to expect that the study has to be terminated due to detrimental effects of the intervention.

This study is financed for two years. If the intended number of participants has not been reached after two years and if no additional financing has been found, the study will be terminated, even if the intended N has not been reached. In that case, the data from the already enrolled participants will still be collected. If the study has to be terminated before the desired number of participants is included, analyses will be conducted with the available quantitative and qualitative data of the participants that did complete the study.

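### Intention to treat is promised in section 10.1, but section 8.7 excludes randomised patients who leave treatment, and the primary analysis set is never defined

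*Combined protocol and SAP*

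**What the plan says.** Section 10.1 gives the analysis principle in one sentence, "Analyses will be done on intention to treat (ITT) basis", and does not define the set. Under research objective 1 it names a repeated-measures linear mixed model and says that this model deals with missing data.

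Section 8.7 says "If patients withdraw from treatment entirely, they will be excluded from the study". It gives as its reason that the module has to be studied as part of ongoing care and adds, for both arms, that when treatment has ended "their data will not be relevant for the research questions of this study".

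Three other places bear on the same patients:

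- Section 8.6 defines drop-out generally as ceasing to answer the questionnaires before the study ends, and adds that "if patients stop using the intervention but still fill out the questionnaire, they are not considered a drop-out". Section 4.4 likewise says that a patient may abandon the module "but can still complete their participation in the study if they fill out all questionnaires".
- Section 8.3, Step 9 (T3), says: "If, at this point, the patient is not being treated at the outpatient clinic anymore, he or she will be contacted by the researchers". By contrast, Step 8 makes being in treatment an explicit condition for the interviews: "Additionally, patients still have to be treated at the outpatient clinic in order to participate".
- Section 8.8, for early stopping only, says "In that case, the data from the already enrolled participants will still be collected", but then words the analysis as one of participants who completed the study.

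**The concern.** Section 8.7 names both arms, so it reaches patients who have already been randomised. Leaving treatment is a post-randomisation event, and section 8.2 states that the trial is not blinded. An analysis that drops leavers no longer compares the groups as randomised, whatever it is called.

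Two things are at stake. First, the primary analysis set is not fixed in advance. One analyst could keep every randomised patient under 10.1 and another could delete leavers under 8.7, and the choice could be made after seeing the data. Second, if exit differs by arm, or if different kinds of patient leave in each arm, deletion can bias the between-arm comparison in either direction.

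**Working it through.** **1. Passages side by side.** Take a patient randomised to either arm who answers T0 and T1 and then leaves treatment entirely.

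| Section | What happens to this patient |
|---|---|
| 10.1 | Analysed, if intention to treat has its usual meaning; the set is not defined |
| 8.7 | Excluded; data called not relevant |
| 8.6 | Not a drop-out if the questionnaires are still answered |
| 8.3, Step 9 | Contacted for T3, if the sentence covers people who withdrew as well as people who finished |

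No section ranks these rules or says whether the T0 and T1 answers are used. Sections 8.6 and 8.7 treat the same person differently: someone who leaves treatment but keeps answering is still a participant under one and is excluded under the other.

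**2. The plan's own figures.** The plan attaches no number to this rule. Its sample size reproduces and is not in dispute: a two-sided t-test at d = 0.5, alpha 0.05 and power 0.80 gives 63.77, so 64 per arm; 128 × 1.2 = 153.6, so 154.

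**3. Illustrative size.** All inputs here are assumptions, because the documents give no exit rates:

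- no true effect;
- patients doing worse are the ones who leave;
- exit after T1, with exit of 15% v 10%, 15% v 5% or 20% v 5% in the two arms;
- correlation rho between staying and the driving variable of 0.3 to 0.5, the same in both arms;
- four waves with unit variance and every pairwise correlation 0.5, so a change score has variance 1 + 1 − 2 × 0.5 = 1.

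The mean shift of the driving variable among stayers is rho × m(p), with m(p) = phi(z)/(1 − p) and z = Phi^-1(p):

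- m(0.05) = 0.1031/0.95 = 0.1086
- m(0.10) = 0.1755/0.90 = 0.1950
- m(0.15) = 0.2332/0.85 = 0.2743
- m(0.20) = 0.2800/0.80 = 0.3500

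Let B be the between-arm difference in this shift:

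| Exit | B, rho 0.3 | B, rho 0.5 |
|---|---|---|
| 15% v 10% | 0.3 × 0.0793 = 0.024 | 0.5 × 0.0793 = 0.040 |
| 15% v 5% | 0.3 × 0.1657 = 0.050 | 0.5 × 0.1657 = 0.083 |
| 20% v 5% | 0.3 × 0.2414 = 0.072 | 0.5 × 0.2414 = 0.121 |

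With equal exit and equal rho, B = 0.

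The effect on the T0-T3 contrast depends on what drives exit:

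- **T1-T0 change (observed).** Its covariance with T3-T0 change is 0.5 − 0.5 − 0.5 + 1 = 0.5, so exclusion gives B/2, or 0.012 to 0.060 SD. If T0 and T1 are kept, the bias is about 0.
- **T3-T0 change (later outcome).** Exclusion gives B, or 0.024 to 0.121 SD. If T0 and T1 are kept, the model predicts T3 from them with coefficients 0.5/1.5 = 1/3 each. Stayers' T3 is shifted by B/2, their T0 by −B/2 and their T1 by 0. The remaining bias is B/2 + (1/3)(B/2) = 2B/3, or 0.016 to 0.080 SD. Keeping the data removes B/3, or 0.008 to 0.040 SD.
- **T1 level.** Its covariance with T3-T0 change is 0.5 − 0.5 = 0, so the bias is about 0 either way.

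Simulation of the four-wave model with known covariance agrees with these values.

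**The case against.** The strongest defence is that 8.7 governs conduct, not analysis. Its heading concerns follow-up, it sits among the withdrawal procedures, and exclusion from the study could mean only that questionnaires stop. Earlier answers would then enter the mixed model with later ones missing, which can be consistent with intention to treat. This reading is possible, so a reader should not infer that 8.7 certainly deletes data collected before exit. But the stated reason is that the data are not relevant, which points to removal, and no section states the milder rule.

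A reader might also infer that Step 9 flatly contradicts 8.7. The documents do not support that much. Section 5.1.2 says that treatment length varies, so a person out of care at week 37 may simply have finished. Yet the closing reason in 8.7 refers to anyone no longer receiving treatment, which blurs the line between finishing and withdrawing. Step 9 therefore adds ambiguity, not a clear contradiction.

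Thirdly, nothing in the documents predicts that exit will differ by arm, and the illustrated bias is modest. That stands, and it limits the argument from size. It does not settle which patients are analysed. Nor are patients who merely stop the module at risk: 4.4, 8.6 and 8.7 all keep them in.

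**Conclusion.** The point holds. As written, the primary analysis set is contradictory and undefined, and following 8.7 literally would drop randomised patients for something that happened after randomisation in an open-label trial. This needs correcting before analysis, whatever the size of any bias.

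Under the assumptions above, exclusion shifts the T0-T3 contrast by about 0.01 to 0.06 SD if exit follows observed early change, about 0.02 to 0.12 SD if it follows the later outcome, and about 0 if it follows T1 level. Keeping pre-exit data removes essentially all of the first but only about a third of the second.

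A reader might infer more from a plain T3 t-test, where 20% v 5% exit and a correlation of 0.5 give 0.12 SD and a type I error of about 11%. That is not the size of this problem. The t-test is only the basis for the sample size in 4.4, the planned analysis is the mixed model, and the figure needs both a 4:1 exit ratio and the strongest assumed selection. The documents do not show that the trial will be biased, or in which direction.

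**What to change.** Wording changes only:

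- In 10.1, define the primary set as all randomised patients, analysed in the arm to which they were randomised, with every collected observation in the mixed model, subject to the deletion requests allowed in 12.1.
- In 8.7, remove the exclusion as far as analysis is concerned, and state that data gathered before exit are retained. The blended-care rationale can be served by an in-treatment analysis, labelled as a sensitivity analysis.
- Reconcile 8.6, 8.7, 10.1 and Step 9 of 8.3, and say whether the Step 9 contact covers patients who withdrew, patients who finished, or both.
- In 8.8, bring the completer wording for early stopping into line with the same set.

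The withdrawal rules in 8.5 stay unchanged. Sending questionnaires after treatment exit is optional and not part of this fix.

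The cost is a protocol amendment, notified to the ethics committee under 12.3, with no new data collection. There is a small downside: the primary estimate will include patients no longer in blended treatment, and bias from exit driven by unobserved later outcomes is reduced but not removed.
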